Hypothesis 3: Compared to the waitlist control group (Group 2), the intervention group (Group 1), the proportion of residents with documented new or changed care planning documents (e.g. advance directive) will increase by 90 days post video viewing.

Specific Aim 3: Describe congruence of preferences observed in the Me & My Wishes video, care conference audio recording, medical record (e.g. POLST), and in family and staff surveys.

PROCEDURES

Training Checklist for Research Staff

Orientation to Project

- CITI/GCP Trainings
- Read: [name] (2015) and [name] (2017) Articles
- Review: R21 Research Plan
- Read: Training Manual Introduction
- ID Badge
- UBox
- IRB (ERIC)
- Encryption
- Skype for Business

Recruitment/Enrollment

- Review Documents: Eligibility Checklist, Demographic & Clinical Information, Consents
- Practice approaching residents and describing the study
- Practice consenting process
- Practice approaching NH staff and families to describe the study
- Practice contacting family/friends via telephone (consent and survey procedures)
- Create a Tickler System/Calendar for MMW video recording, care conference and follow ups

Video Production

- Practice facilitating the Conversation Guide
- Video Recording and Equipment
- Video Editing (see detailed process on page X)

Data Collection & Management

Cloud Storage

- REDCap: Orientation, Survey Entry and Data Management
- Data Security: Information Storage and Confidentiality
- REDCap participant tracking (enrollment, refusals, withdraws)
- Participant Tracking: IDs, Calendar, Study Enrollment

Nursing Facility (Site)

- Discuss how to perform the Chart Review
- Practice administering the Resident Surveys (baseline, time of sharing, 90 days)
- Discuss the logistics of administering the Staff and Family surveys in care conference
- Discuss how to set up Care Conference Audio Recording and Equipment
- Practice administering Staff and family surveys (baseline, time of sharing, 90 days)

Data Analysis

- Audio Transcription and verification
- REDCap – how to run reports (e.g. accrual reports)
- NVivo – (e.g. uploading documents, coding)

Chapter Three

Eligibility, Recruitment and Enrollment

Eligibility Criteria

Use the Eligibility Checklist (Appendix A) to document whether selected residents are eligible to participate in this study or not.

❖ Resident Inclusion Criteria

We will include assisted living (AL) residents in addition to nursing home (NH) residents. Inclusion criteria:

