We track two admission dates (initial admission date and most recent admission date). Please calculate length of stay from both these dates.

7. What is the best way to find the Advance Directive information?

This depends. Some charts have this information on the demographic tab and Documents tab and some only have this information on the POLST form. You will need to look carefully in multiple places. POLST may be a separate document on its own. Once you find the form, you will need to look at it carefully to find the rest of the information.

8. I found the care plan but I'm not sure if the goals for the care are consistent with resident preferences.

You may or may not find evidence of resident preferences written on the care plan. Review the care plan carefully and look for any evidence that is consistent with the resident preferences such as resident statements – this may be written in quotes.

9. Could there be any other place where the resident preferences is documented?
Yes. There may be a standardized document that has the resident preferences. If the facility has such as form, you will need to include the source and location of information.

10. When I do a 90-day follow-up data extraction on the same chart, how do I get access to the chart and what is the procedure?
You will need to notify the NH administrator ahead of time about your intent and when you will be at the facility. Other than that, you will follow the same procedure outlined on the data extraction protocol for initial Demographic and Medical Record Review Forms.

Participant Confidentiality

Participant identification (ID) numbers will be assigned for all individuals approached to track those who enroll and those who decline. Study sites will be randomly assigned to an intervention or wait-list control group. Use the REDCap database to track all individuals (even though who decline). This number will be used instead of the participant's name on all forms and tracking. Write the participant ID on the top right hand corner of all documents except for the consent forms.

Data Security

- ❖ Documents
Consent forms are stored separately from all other recruitment and enrollment documents, including surveys where appropriate.
- ❖ Audio Recordings
Audio recordings are to be uploaded to the appropriate folder on UBox, then deleted from the audio recorder. Audio recordings are deleted once transcription has been completed, compared to audio recording, and finalized.

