- ❖ Chain of Custody Documentation
Use the Chain of Custody forms to document exchange of the audio recorders, laptops and video equipment. The form must be filled out completely, including the name of the person in custody of the equipment and the dates in which the possession occurred.

Withdrawal of Participation / Attrition

Document any withdrawals of participation in REDCap along with reason.

Chapter Four

Administering Surveys

Surveys will be administered to residents, staff and family at three time points (baseline, sharing/within 72 hours of sharing, and 90 days post sharing).

Resident Surveys

The Resident Baseline Survey will need to be collected at the time of enrollment and read aloud to the resident. Follow same procedures for time of sharing and 90-day surveys.

Care Conference Staff Surveys (Time of sharing the video)

The Care Conference Staff Baseline Survey is provided at the time of enrollment (at a staff meeting or care conference prior to video sharing).

Family Surveys

The family baseline survey will need to be completed at the time of enrollment. Except for consent, follow same procedures for completing time of sharing and 90 day surveys.

Care Conference Staff and Family Compensation

Facility staff and family members are compensated with a \$5 gift card following the completion of each survey taken. If family are not present at care conference, their gift card can be mailed/mailed.

Care Conference Audio Recording and Data Collection Procedures

Care conference at the time of sharing will be audio-recorded using two audio recorders.

Most likely, staff and family caregivers will have completed the consent process at the time of the care conference meeting when the video is shared. In the event that an individual has not been consented (e.g. new staff to the care conference team), we will meet with the individual in a private space to review the recruitment letter and caregiver consent and upon agreement the informed consent process will be completed prior to starting the meeting.

Care Conference Video Sharing and Survey Collection Guidance

Briefing points for team member facilitating video sharing and discussion

- SC turn on/off 2 audio recorders.
- Let participants know video is approx. 20min, opportunity for discussion at end of video facilitated.

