- At end of video sharing the care conference team member facilitator will **prompt conversation** with care conference participants to identify the most important aspects of the video to be discussed and addressed in the care plan.
- At end of video/discussion, please give each participant **a post video sharing survey** (staff or family member surveys depending on who is present). Once completed please collect and put in a sealed envelope
- Please give the **envelope and audio recorders** to the SC who will be waiting outside the room
- Provide **gift cards** for staff and family members

Chapter Five

Facilitating the Conversation

Role of the facilitator:

While any one can have this type of conversation with an older adult, there are a few things to be aware of when in the role of facilitator. It is common to feel like there needs to be a resolution; a way to address the resident's wish not to have any treatment or to offer solutions when further discussion or a change in the advance directive is warranted. For the purposes of this study, however, the main objective is to enhance communication and promote conversation. Be aware of your own background, opinions and experiences and reflect on how that might affect this role. The facilitator of the *Me & My Wishes* conversation must possess the following attributes:

- Knowledge:
 - Basics of nursing homes and end-of-life care and processes.
 - Physical aspects of ageing and the care of older individuals.
- Modeling:
 - Demonstrate warm, compassionate and patient communication.
 - Attention - Acknowledge the individual by showing appreciation and respect.
Show affection by providing comfort and presence.
 - Acceptance of the person and their preferences.
- Skills:
 - Listening skills.
 - Self-awareness.
 - Flexibility.
- Values:
 - Empathy.
 - Genuineness.
- Style:
 - Use personal communication style to enhance authenticity. Emotions of all kinds may be triggered (sadness, happiness, laughter, joy, fear, anger).

❖ Use the following checklist to guide the facilitator training process:

Create a training schedule that includes the following steps in order:

- 1) Review of the Conversation Guide as a group. Practice reading questions and incorporating the probes.
- 2) Practice facilitating with three people, each take a turn being the facilitator and the resident, using resident roles (see below). Repeat this process at least 2-3 more times.

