## Goals of Care

We analyzed results with an intent to treat approach using SPSS Version 24.0 (SPSS, Armonk, NY). Multilevel logistic regression (generalized estimating equations [GEE] with an autoregressive (1) working correlation matrix, logit link function) were fitted to assess the primary hypotheses. The models account for the repeated measures (3 or 4 time points), correlated, data structure per person. An additive model was conducted with contrast coding for each time point, treatment, and follow-up effects.

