### **Concordance Analysis**

Analyses were conducted using SPSS Version 24.0 (SPSS, Armonk, NY) using an intent to treat approach. Multilevel linear regressions (generalized estimating equations [GEE] with an autoregressive (1) working correlation matrix) were fitted to assess concordance of preferences between the resident videos and staff and family surveys at three (intervention group) or four (wait-list control group) time points. The models account for the repeated measures (three or four time points), correlated, data structure per person. Because this study used a waitlist control design, data includes the initial baseline data for both groups and second baseline data for the waitlist group. An additive model was conducted with contrast coding for each time point, treatment, and follow-up effects. This allowed us to compare the groups by the different times they received the video, with Time 1 (Baseline) as the reference category. For example, a participant in the Immediate group at time of video sharing would receive contrast coding: Time 2 (1); Time 3 (0), Time 4 (0), Treatment (1), Follow-up (0). While a participant in the Wait-list (Control) group at time of video sharing would receive contrast coding: Time 2 (0), Time 3 (1), Time 4 (0), Treatment (1), Follow-up (0). We stratified our analysis by the three different types of participants - residents, family members, and staff members.

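### The protocol schedules three surveys for everyone and omits the wait-list second baseline on which the SAP's GEE models depend

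*Protocol*

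**What the plan says.** **Protocol**

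- The survey section of Chapter Four gives a single schedule: "Surveys will be administered to residents, staff and family at three time points (baseline, sharing/within 72 hours of sharing, and 90 days post sharing". There is no exception for the wait-list. The resident baseline belongs to enrolment, before any delay: "The Resident Baseline Survey will need to be collected at the time of enrollment and read aloud to the resident". The staff and family baselines are also tied to enrolment.
- Training checklist, Nursing Facility (Site): "Practice administering the Resident Surveys (baseline, time of sharing, 90 days" and "Practice administering Staff and family surveys (baseline, time of sharing, 90 days". Again there are three waves.
- Chapter Four, guidance on video sharing: "At end of video/discussion, please give each participant" introduces the post-video survey, so staff and family at the conference have seen the video when they answer it.
- Chapter Three, data-extraction FAQ: "When I do a 90-day follow-up data extraction on the same chart" is the only later chart extraction named.

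**SAP**

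- Randomization: Group 1 views within three months of baseline. Group 2 views within three months after a delayed start whose length is not given.
- Goals of Care: "The models account for the repeated measures (3 or 4 time points), correlated, data structure per person".
- Concordance Analysis: three time points for the intervention group and four for the wait-list, and "data includes the initial baseline data for both groups and second baseline data for the waitlist group". Sharing is coded at Time 2 for Group 1 and at Time 3 for Group 2, so Group 2's Time 2 is the pre-sharing second baseline.
- Primary & Secondary Outcomes, and Power and Sample Size: baseline, 3 months and 6 months for both groups. This is a third version of the schedule.

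**The concern.** A wait-list design draws its control information from people who have been enrolled for some time and are still unexposed. On the protocol's schedule no survey observes anyone in that state: each Group 2 participant's first survey after enrolment is at sharing. The second baseline in the SAP is the one observation that would fill the gap, and the protocol neither schedules nor dates it.

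The outcomes at stake are those measured by survey: self-reported conversations (part of Hypothesis 1), self-efficacy (Hypothesis 2), and the staff and family surveys used for concordance. A survey not taken before exposure cannot be taken afterwards.

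**Working it through.** **1. The plan's own figure.** The SAP states a detectable f of .213 with N = 48, 2 groups, 3 time points, correlation .5, power .90 and alpha .05. For the within-between interaction, λ = f²·N·m/(1 − ρ) = 0.213² × 48 × 3/0.5 = 13.07, with df1 = (2 − 1)(3 − 1) = 2 and df2 = (48 − 2)(3 − 1) = 92. The noncentral F distribution gives power 0.8998, so the figure reproduces. It assumes three time points common to both groups. That matches neither the 3-or-4-point GEE nor the protocol's visits, which are anchored on sharing.

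**2. The GEE design.** The parameters are the intercept a, time effects t2, t3 and t4, Treatment d and Follow-up φ, six in all. The two sharing rows are printed under Concordance Analysis, and Time 1 is the reference. The 90-day rows are not printed, so I take Follow-up = 1 and Treatment = c, and try c = 0 and c = 1. I assume that the Goals of Care model uses the same coding, since its description matches. With a logit link the argument applies to the linear predictor.

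| Cell | Linear predictor |
|---|---|
| Group 1, Time 1 baseline | a |
| Group 1, Time 2 sharing | a + t2 + d |
| Group 1, Time 3 90 days | a + t3 + c·d + φ |
| Group 2, Time 1 baseline | a |
| Group 2, Time 2 second baseline | a + t2 |
| Group 2, Time 3 sharing | a + t3 + d |
| Group 2, Time 4 90 days | a + t4 + c·d + φ |

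**3. Rank and estimability of Treatment, the same for c = 0 and c = 1.**

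| Data | Rank | Treatment |
|---|---|---|
| All seven cells | 6 of 6 | estimable |
| Without Group 2's second baseline | 5 of 6 | not estimable |
| Three protocol visits labelled Times 1–3 in both groups | 3 of 5 | not estimable |

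In the second row six cells remain, but the two baseline rows are identical, leaving five distinct rows for six parameters. Adding 1 to d, subtracting 1 from each of t2, t3 and t4, and adding 1 to φ when c = 0 (0 when c = 1) leaves every fitted value unchanged. Treatment is therefore indistinguishable from a time trend. Adding a group main effect does not help: the rank is 6 of 7 and Treatment is still not estimable.

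**4. Where the information comes from.** With all seven cells, d is identified by (Group 1, Time 2) − (Group 2, Time 2). As an illustration, take a continuous outcome, 24 per group, AR(1) correlation 0.5 and no clustering. The standard error of d is then √(2 × (1 − 0.5²)/24) = 0.25 SD. Without the second baseline there is no estimate to attach a standard error to.

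**5. The group-by-time model.** This is the SAP model under Primary & Secondary Outcomes and the only one that names self-efficacy. With visits aligned on sharing it has six cells and rank 6 of 6, so it can be fitted, but both groups are exposed at both later visits. On calendar time, assume that Group 2's sharing falls near 6 months. Group 2 then has no 3-month cell and the rank is 5 of 6. The 3-month interaction is not estimable. The 6-month interaction is estimable, but it compares Group 1 with a group that has just been exposed.

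**6. What the second baseline does not supply.** Hypotheses 1 and 2 are set at 90 days after viewing. At Group 1's 90-day visit (Time 3), Group 2 is already at sharing. The 90-day effect c·d + φ equals (Group 1, Time 3 − Group 2, Time 3) + (Group 1, Time 2 − Group 2, Time 2) under either value of c. That sum is valid only if the sharing effect is the same in both groups and at both times.

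**The case against.** The strongest reply is that the SAP says second-baseline data are in the dataset, and that its GEE sections are written largely in the past tense. A reader might infer from the protocol that the survey was never taken; the documents do not support that. The protocol reads as a training manual, and the survey appendices and research plan it cites are not available here, so absence from every site instruction is not shown. The SAP's 3-month point might also be Group 2's pre-sharing measurement. That is an inference, because the length of the delay is not stated. What remains is that Chapter Four lists its survey times as complete, the checklist agrees, and neither contains the wave. Chapter Three asks staff to record control-group members who lose eligibility after the delay, but it attaches no survey to that contact.

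A reader might also infer that no treatment effect in the SAP can be estimated, including the one on self-efficacy. Non-estimability is shown only for the additive GEE coding. For the group-by-time model aligned on sharing, the difficulty is what the estimate means.

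Two further replies stand in part. Dated chart entries may allow documented goals-of-care discussions to be rebuilt for the delay period, which partly protects chart outcomes. A linear time trend would make Treatment estimable without the second baseline (rank 4 of 4), but only through that assumption, and the SAP specifies a separate term for each time point.

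**Conclusion.** The protocol and SAP contradict each other on how many times wait-list participants are surveyed, and the missing wave is the one that identifies Treatment in the SAP's GEE models. If sites follow the protocol, Treatment in that coding is not estimable (rank 5 of 6) for self-reported conversations and for staff and family concordance. The group-by-time model for self-efficacy remains computable with sharing-aligned visits, but it does not give the comparison with an unexposed control that Hypothesis 2 describes.

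This rests on the printed coding, on Follow-up = 1 at 90 days, and on Goals of Care using the same coding as Concordance Analysis. It does not depend on how Treatment is coded at 90 days. It would also be too strong to infer that adding the survey restores a concurrent control for the 90-day effects. It does so at Group 1's sharing visit only.

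**What to change.** 1. Amend Protocol Chapter Four and the training checklist so that Group 2 residents, staff and family have four survey points: baseline, a second baseline before any exposure, sharing, and 90 days after sharing.
2. Date the second baseline from enrolment, with a window matched to the elapsed time of Group 1's sharing survey, and state the length of the delay. Add a chart extraction for Group 2 at the same point.
3. Use the same visit definitions in the SAP's Primary & Secondary Outcomes, Power and Sample Size, Goals of Care and Concordance Analysis sections, and print the coding of the second-baseline and 90-day rows.
4. State in the SAP that the concurrent unexposed control exists only at Group 1's sharing visit, and that the 90-day effect relies on a sharing effect common to both groups and times.
5. If the survey was in fact taken, record when, and report its completion.

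The cost is a protocol and checklist amendment, one more short survey round in Group 2 (with the existing $5 gift card for staff and family) and one chart extraction. The SAP already assumes the survey data. The downside is the added burden on wait-list participants.

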- NH champion speaks to resident with no bias introduced (such as "this resident would be a good person for this study").
- Only SC's explain MMW study to resident.
- Does NH champion know of any additional people coming to care conference that are not aware of study?
- When calling NH champion confirm residents are available for consenting/video recording.
- Ask if there are any recent admissions that would meet criteria.

Family Consent and Survey Scripting

A recruitment letter and a copy of family caregiver consent will be sent either by mail or email to the family members identified by the resident stating the purpose of the study and that a follow-up phone call will be made. The letter will include information of who to contact if they wish to opt out. If the family member declines we can ask the resident if they want to share the video with anyone else

- ❖ Family (process for contacting/recruitment)
Family Recruitment and Consent Letters (Appendix G)
Family Sub Study Consent Letter (Appendix G1)

This process should be practiced with a member of the MMW team prior to live implementation.

Hello is this (family member's name)?—response.

This is (your name) from the University of Utah College of Nursing and the Me & My Wishes project. I am calling to verify that you received the letter about the project and to see if you have some time today to learn more about the project. Is this a good time?—response.

At this point in the conversation please refer to the *Family Consent Cover Letter*. Proceed by reading the first two paragraphs of the consent.

Does this sound like something that you would be interested in?—response.

If yes: Great, thank you. Let's take the next few minutes to review more details about the study, your participation, and obtain your consent to participate. If you would like, I can send you a copy of the consent via mail/email?—response.

Do you have 15-20 minutes now to go over the initial survey?—response.

Proceed to the family baseline survey.

Do you have any questions?—response. (answer questions). If mail/email address is not known, obtain for the purposes of sending \$5 gift certificate.

Outline the next steps for the participant.

As mentioned in the consent you may watch your family member's/friends personal video by attending care conference at the facility or at the time that we share the video I can send you a link to view the video from your home computer and complete a brief survey.—response.

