How to send a resident video and follow-up survey using REDCap

Log in to REDCap → Select/click on Me & My Wishes: Feasibility and Acceptability → In the left tool bar select/click on Record Status Dashboard → In column 7 of the spreadsheet find *Family Post Video-Viewing Survey* → Scroll down to the appropriate participant/record ID number → click on the clear circle (the following screen will appear)

Click on the drop-down tab labeled *Survey options* → Select *Open Survey* → a window web browser will open with the participant's video and follow up survey → copy and paste the URL into the following email template:

Dear (Name) –

Below is the link to the Me & My Wishes video of your family member/friend. Please view the video and complete the corresponding survey. You may open the survey in your web browser by clicking the link below:

[Family Post Video-Viewing Survey](#)

If the link above does not work, try copying the link below into your web browser:

[\[insert link\]](#)

Please contact me or [name] (cc'd on the email) if you need help accessing and viewing the video.

This link is unique to you and should not be forwarded to others. The family consent form reviewed with you on the telephone is attached.

Thank you so much!

Name

Title

Make the necessary updates—participant name, and your name and title → Remove the survey/video link in the template (highlighted yellow) → Replace with previously copied URL → Create a hyperlink for the section highlighted in pink (see the next section for instruction on how to create a hyperlink) → Send email.

Creating a Hyperlink in Outlook

Select the following text in the email *Family Post Video-Viewing Survey* → In the email window task bar, next to font color, (show below) click on the globe icon with chain. Paste the URL and click ok → You have created a hyperlink!-->

Chapter Eight

Unanticipated Problems and Events

Unanticipated Problems

The University of Utah requires investigators to report all potential unanticipated problems and events to the IRB. Unanticipated problems (UPs) are defined as any incident, experience or outcome that meets all of the following criteria:

- Unexpected (unforeseen by the researcher or the research participant) in terms of nature, severity, or frequency, given the research procedures and the subject population being studied;

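### Home-viewing relatives can answer the post-video survey with the video at hand, and any gain from that enters the family concordance Treatment contrast

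*Protocol*

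**What the plan says.** **Delivery at home.** Protocol Chapter Seven (Family Post Video-Viewing Survey) has staff open the REDCap survey, whereupon "a window web browser will open with the participant's video and follow up survey". They paste that single address into an e-mail; the template step reads "Remove the survey/video link in the template (highlighted yellow"). The relative is told: "Please view the video and complete the corresponding survey". No separate survey page, replay limit, link expiry or request to answer unaided is stated.

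**Choice of mode.** The script in Chapter Three (Family Consent and Survey Scripting) says "you may watch your family member's/friends personal video by attending care conference at the facility", or by a link used at home together with a short survey. At the care conference, Chapter Four's guidance puts the survey last: "At end of video/discussion, please give each participant" the form.

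**Timing.** Chapter Four sets "three time points (baseline, sharing/within 72 hours of sharing, and 90 days post sharing"). The family baseline is taken at enrolment. The script does it by telephone ("Do you have 15-20 minutes now to go over the initial survey"), before any video is shared.

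**Analysis.** The SAP's Concordance Analysis fits linear GEE models "to assess concordance of preferences between the resident videos and staff and family surveys at three (intervention group) or four (wait-list control group) time points". Sharing rows are coded Treatment 1, Follow-up 0 in both groups. Residents, family and staff are modelled separately, and there is no term for viewing mode.

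**The concern.** The video is both the intervention and the answer key. At baseline a relative has only prior knowledge to draw on. At the care conference the relative answers after the showing. At home the relative may answer while able to return to the video. Concordance at sharing can then rise because the relative learned the preferences, or because they were looked up, and the model cannot separate the two.

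If having the video available changes agreement with it, the change can plausibly only be upward. At stake is the meaning of the family Treatment coefficient. Read as knowledge gained by the family, it may be too large. That reading matters because relatives cannot be expected to have the video open when a real decision arises.

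**Working it through.** **1. The plan's own figure.** The only quantitative claim is in the SAP's Power and Sample Size section: N = 48, 2 groups, 3 time points, correlation 0.5, alpha 0.05, f = 0.213 at power 0.90. With λ = f²·N·m/(1−ρ) = 0.213² × 48 × 3 / 0.5 = 13.07 on 2 and 92 degrees of freedom, power is 0.8998; solving for 0.90 gives f = 0.2131. The figure reproduces. It concerns the group-by-time interaction, not family concordance, and this point does not touch it.

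**2. Where the bias enters.** The SAP gives the coding of the two sharing rows. The remaining rows below are my reading of its three or four time points.

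| Group | Time 1 | Time 2 | Time 3 | Time 4 |
|---|---|---|---|---|
| Early | baseline | sharing (Treatment 1) | 90 days | – |
| Wait-list | baseline | second baseline | sharing (Treatment 1) | 90 days |

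Let h be the share of relatives viewing at home and g the mean extra concordance among them from having the video available. The sharing rows then carry a bias b = h × g: b1 in the early group, b2 in the wait-list group. All other rows carry none, if the 90-day survey is answered without the video.

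Solving the additive model for the bias alone:

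- Intercept = 0, from the baseline rows.
- Time 2 = 0, from the wait-list second baseline.
- Time 2 + Treatment = b1, so Treatment = b1.
- Time 3 + Treatment = b2, so Time 3 = b2 − b1.
- Follow-up, from the early group's 90-day row: b1 − b2 if Treatment is coded 0 there, or −b2 if Treatment stays at 1.

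With b1 = b2 = b, the whole of b goes into Treatment, and Follow-up shifts by 0 or by −b according to a coding that the SAP does not give. A numerical fit with one unit of bias on the sharing rows agrees: the Treatment coefficient is 1.0 under least squares and under AR(1) correlations of 0.3, 0.5 and 0.7, and Follow-up is 0 or −1.0. The wait-list crossover does not cancel the bias, because its sharing row is exposed as well.

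**3. The 90-day total effect.** This is Follow-up alone when Treatment is 0 on 90-day rows, and Treatment + Follow-up when it is 1. Its bias is b1 − b2 under either coding, so it is zero when the two groups are alike in h × g.

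**4. Size.** Neither h nor g is in the documents. Purely as assumptions, on a proportion scale, h × g is:

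| h | g = 0 | g = 0.10 | g = 0.30 |
|---|---|---|---|
| 0.25 | 0 | 0.025 | 0.075 |
| 0.50 | 0 | 0.05 | 0.15 |
| 1.00 | 0 | 0.10 | 0.30 |

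The first column is as compatible with the documents as the others.

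**The case against.** **The survey mode is not settled.** Chapter Four tells staff to use the baseline procedure, apart from consent, for the later family surveys. The scripted baseline is a telephone interview, which would remove the combined page. This stands as a conflict within the protocol. It does not dispose of the point, because both Chapter Three and Chapter Seven describe completion through the home link.

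**Chapter Seven may be carried over.** It directs staff to a REDCap project named for feasibility and acceptability, whereas this is the efficacy stage. But the current Chapter Three script also promises a home link with a survey, so the arrangement is not merely a leftover.

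**Nothing shows that relatives look back.** The survey items, the page layout and whether the video stays playable are not shown. Finding an answer in a video of about 20 minutes takes effort. This stands: a reader might infer that these scores are open-book and that the effect is overstated by some multiple. The documents support only that open-book answering is possible. A multiple would need an agreement rate, a look-back rate and a true gain, and none is given.

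**False decay at 90 days.** A reader might also infer that a later fall would be misread as fading knowledge. That follows for the Follow-up coefficient only if Treatment stays at 1 on the 90-day rows, and that coding is unstated.

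**Comparison with staff.** The SAP models the strata separately and plans no test between them, so no planned comparison is spoiled.

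**Low stakes, and partly a choice of estimand.** Aim 3 is worded as description and carries no hypothesis, and home access is part of the intervention. This stands and limits the weight of the point. However, the SAP fits a Treatment contrast to concordance, so what that contrast measures should be clear.

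**Conclusion.** The point holds as a possible, one-directional measurement artefact. Home viewers can answer with the scoring reference at hand, while baseline respondents and conference attendees cannot. Any resulting gain passes in full into the family Treatment coefficient. With similar groups the bias is h × g, from zero upward, and the documents allow no firmer figure. This rests on the combined page being used in this trial, on the sharing-time family survey holding the preference items (which the SAP's time points imply but no instrument shows), and on the row layout set out above.

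The reach is narrow: the family concordance analysis under Aim 3. Hypotheses 1 to 3, the resident and staff models and the sample-size figure are unaffected. Self-efficacy is not scored against the video. This is a cheap improvement worth making, and no threat to the trial's main conclusions.

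**What to change.** 1. **Protocol Chapter Seven.** Put the survey on its own page or link without the video, released once the video page is submitted, with an instruction to answer from memory. Reconcile this with the Chapter Four direction to reuse the baseline procedure, so that one mode is stated for the sharing survey.
2. **Data collection.** Record for each relative whether viewing was by home link or at the care conference.
3. **SAP, Concordance Analysis.** In the family model, add a sensitivity analysis that excludes, or adjusts for, sharing-time surveys completed on the combined page. State that viewing mode is self-selected, so this is a check and not a corrected estimate.
4. **Retained knowledge.** Base any such claim on the 90-day total effect, with that survey given without the video, and state how Treatment is coded on the 90-day rows. Report home-viewing shares by group, since an imbalance would leave b1 − b2 in this effect.

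The cost is a REDCap set-up change, a revised e-mail, one more click or call, and perhaps slightly more non-response at sharing. The SAP describes this analysis in the past tense. If collection is complete, items 3 and 4 remain: the sensitivity analysis needs viewing mode to be recoverable, and the 90-day claim needs that survey to have been answered without the video.
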